**Table 6-4 Criteria for interruption and re-initiation of LDK378 treatment**

| Worst toxicity (CTCAE 4.03 Grade)*  | Dose Modifications for LDK378   |
|--|--|
| HEMATOLOGICAL   |  |
| Neutropenia (ANC)   |  |
| Grade 1 (ANC < LLN - $1.5 \times 10^9/L$ )
Grade 2 (ANC < 1.5 and $\geq 1.0 \times 10^9/L$ )
Grade 3 (ANC < 1.0 and $\geq 0.5 \times 10^9/L$ )                       | Maintain dose level  |
| Grade 4 (ANC < $0.5 \times 10^9/L$ )   | Omit dose until resolved to $\leq$ Grade 2, then:
If resolved in $\leq 7$ days, then maintain dose level
If resolved in $> 7$ days, then $\downarrow 1$ dose level |
| Febrile neutropenia
(ANC < $1.0 \times 10^9/L$ , with a single temperature of $\geq 38.3$ °C or a sustained temperature of $\geq 38$ °C for more than one hour ) | Omit dose until clinically resolved and neutropenia $\leq$ Grade 2, then $\downarrow 1$ dose level   |
| Thrombocytopenia  |  |
| Grade 1 (PLT < LLN - $75 \times 10^9/L$ )
Grade 2 (PLT < 75 and $\geq 50 \times 10^9/L$ )   | Maintain dose level  |
| Grade 3 (PLT < 50 and $\geq 25 \times 10^9/L$ )  | Omit dose until resolved to $\leq$ Grade 2, then:
If resolved in $\leq 7$ days, then maintain dose level
If resolved in $> 7$ days, then $\downarrow 1$ dose level |
| Grade 4 (PLT < $25 \times 10^9/L$ )  | Omit dose until resolved to $\leq$ Grade 2, then $\downarrow 1$ dose level   |
| HEPATIC   |  |
| Alkaline phosphatase and/or Gamma-glutamyl transpeptidase (GGT)   |  |
| Isolated elevations of any grade   | Maintain dose level  |
| Total Bilirubin**
(for patients with Gilbert Syndrome these dose modifications apply to changes in direct [conjugated] bilirubin only)                           |  |
| Grade 1 ( $> ULN$ and $\leq 1.5 \times ULN$ )  | Maintain dose level with liver function test (LFTs)*** monitored as per protocol   |

| Worst toxicity (CTCAE 4.03 Grade)*   | Dose Modifications for LDK378  |
|---|---|
| Grade 2 (> 1.5 and ≤ 3.0 x ULN) with ALT or AST ≤ 3.0 x ULN   | Omit dose until resolved to ≤ Grade 1, then:
If resolved in ≤ 7 days, then maintain dose level
If resolved in > 7 days, then ↓ 1 dose level   |
| Grade 3 (> 3.0 and ≤ 10.0 x ULN) with ALT or AST ≤ 3.0 x ULN  | Omit dose until resolved to ≤ Grade 1, then:
If resolved in ≤ 7 days, ↓ 1 dose level
If resolved in > 7 days, discontinue patient from LDK378 |

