| Grade 4 (> 10.0 x ULN)  | Permanently discontinue patient from LDK378   |
| AST or ALT   |   |
| Grade 1 (> ULN and ≤ 3.0 x ULN)   | Maintain dose level with LFTs*** monitored per protocol   |
| Grade 2 (> 3.0 and ≤ 5.0 x ULN) without total bilirubin elevation to > 2.0 x ULN  | Maintain dose level with LFTs*** monitored per protocol   |
| Grade 3 (> 5.0 and ≤ 20.0 x ULN) without total bilirubin elevation to > 2.0 x ULN   | Omit dose until resolved to ≤ Grade 1, then ↓ 1 dose level  |
| Grade 4 (> 20.0 x ULN) without total bilirubin elevation to > 2.0 x ULN   | Omit dose until resolved to ≤ Grade 1, then ↓ 1 dose level  |
| AST or ALT and concurrent Total bilirubin  |   |
| AST or ALT > 3.0 x ULN with total bilirubin > 2.0 x ULN in the absence of cholestasis or hemolysis  | Permanently discontinue patient from LDK378. Refer to Section 6.3.2.2 for additional follow-up.                                     |
| AST or ALT > 5.0 and ≤ 20.0 x ULN with total bilirubin > 1.5 and ≤ 3.0 x ULN  | Permanently discontinue patient from LDK378 if event reoccurs after dose reduction.   |
| PANCREATIC   |   |
| Amylase and/or lipase evaluations (in absence of clinical symptoms)   |   |
| Grade 1 (> ULN and ≤ 1.5 x ULN)   | Maintain dose level   |
| Grade 2 (> 1.5 - 2.0 x ULN)   | Maintain dose level   |
| Grade ≥ 3 (> 2.0 x ULN)   | Omit dose until resolved to ≤ Grade 1, then ↓ 1 dose level  |
| Note: Withhold LDK378 for acute onset of new or progressive unexplained abdominal symptoms, such as severe pain or vomiting; perform diagnostic procedures (e.g., abdominal CT scan or ultrasound) to exclude pancreatic pathology. |   |
| RENAL  |   |

| Worst toxicity (CTCAE 4.03 Grade)*               | Dose Modifications for LDK378  |
|---|---|
| Serum creatinine                                 |   |
| Grade 1 (>1 and ≤1.5 x baseline; >ULN and ≤ 1.5 x ULN)  | Maintain dose level   |
| Grade 2 (>1.5 and ≤3.0 x baseline; > 1.5 and ≤ 3 x ULN) | Omit dose until resolved to ≤ Grade 1, then:
If resolved in ≤ 7 days, then maintain dose level
If resolved in > 7 days, then ↓ 1 dose level                         |
| Grade 3 (>3.0 x baseline; > 3.0 and ≤ 6.0 x ULN)        | Omit dose until resolved to ≤ Grade 1, then ↓ 1 dose level  |
| Grade 4 (> 6.0 x ULN)                                   | Permanently discontinue patient from LDK378   |
| GASTROINTESTINAL                                 |   |

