| Diarrhea****                                     |   |
| Grade 1   | Maintain dose level but adjust anti-diarrhea treatment  |
| Grade 2 (despite maximal anti-diarrheal medication)     | Omit dose until resolved to ≤ Grade 1, then maintain dose level.
If diarrhea returns as ≥ Grade 2, then omit dose until resolved to ≤ Grade 1, then ↓ 1 dose level     |
| Grade 3 (despite maximal anti-diarrheal medication)     | Omit dose until resolved to ≤ Grade 1, then ↓ 1 dose level  |
| Grade 4 (despite maximal anti-diarrheal medication)     | Omit dose until resolved to ≤ Grade 1, then ↓ 1 dose level  |
| Nausea*****                                      |   |
| Grade 1 or 2  | Maintain dose level but adjust anti-emetic treatment  |
| Grade 3 (despite standard anti-emetics)                 | Omit dose until resolved to ≤ Grade 1, then ↓ 1 dose level  |
| Vomiting*****                                    |   |
| Grade 1   | Maintain dose level but adjust anti-emetic treatment  |
| Grade 2 (despite standard anti-emetics)                 | Omit dose until resolved to ≤ Grade 1, then maintain dose level.
If vomiting returns as ≥ Grade 2, then suspend dose until resolved to ≤ Grade 1, then ↓ 1 dose level. |
| Grade 3 (despite standard anti-emetics)                 | Omit dose until resolved to ≤ Grade 1, then ↓ 1 dose level  |
| Grade 4 (despite standard anti-emetics)                 | Omit dose until resolved to ≤ Grade 1, then ↓ 1 dose level  |
| METABOLIC  |   |
| Any Grade hypophosphatemia                       | Treatment with phosphate supplements as clinically indicated and maintain dose level  |

| Worst toxicity (CTCAE 4.03 Grade)*   | Dose Modifications for LDK378  |
|---|---|
| Persistent hyperglycemia (glucose > 250 mg/dL) despite optimal anti-hyperglycemic therapy  | Omit dose until hyperglycemia is adequately controlled then resume LDK378 at ↓ 1 dose level
If adequate hyperglycemic control cannot be achieved with optimal medical management permanently discontinue patient from LDK378 |
| GENERAL DISORDERS  |   |
| Fatigue (asthenia)   |   |
| Grade 1 or 2  | Maintain dose level   |
| Grade 3   | If grade 3 fatigue resolves to Grade 2 in ≤ 7 days, maintain dose level
If grade 3 fatigue lasts > 7 days, omit dose until resolved to ≤ Grade 2 and then ↓ dose level   |
| PULMONARY  |   |
| Notes:  |   |

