| Grade 1 or Grade 2  | Omit dose until recovery to asymptomatic bradycardia or to a heart rate $\geq$ 60 bpm
Evaluate concomitant medications known to cause bradycardia and adjust the dose of LDK378  |
| Grade 3   | Omit dose until recovery to asymptomatic bradycardia or to a heart rate $\geq$ 60 bpm
Patient may resume LDK378 at $\downarrow$ 1 dose level with frequent monitoring  |
| Grade 4 (in patients taking a concomitant medication also known to cause bradycardia or a medication known to cause hypotension)                                | Omit dose until recovery to asymptomatic bradycardia or to a heart rate $\geq$ 60 bpm
If the concomitant medication can be adjusted or discontinued, resume LDK378 at $\downarrow$ 1 dose level with frequent monitoring   |
| Grade 4 (in patients who are not taking a concomitant medication also known to cause bradycardia or known to cause hypotension)                                 | Permanently discontinue patient from LDK378   |

| Worst toxicity (CTCAE 4.03 Grade)*  | Dose Modifications for LDK378 |
|--|--------------------------------------|
| 
* Common Terminology Criteria for Adverse Events (CTCAE) version 4.03. All dose modifications should be based on the worst preceding toxicity.
 
** If Grade 3 or 4 hyperbilirubinemia is due to the indirect (non-conjugated) component only, and hemolysis as the etiology has been ruled out as per institutional guidelines (e.g., review of peripheral blood smear and haptoglobin determination), then ↓ 1 dose level and continue treatment at the discretion of the Investigator.
 
***LFTs include albumin, ALT, AST, total bilirubin (fractionated if total bilirubin > 2.0 x ULN), alkaline phosphatase
 
**** Dose modifications apply to patients who experience diarrhea despite appropriate antidiarrheal medication. This medication should be started at the first sign of abdominal cramping, loose stools or overt diarrhea (see Section 6.3.2.5)
 
***** Dose modifications apply to patients who experience nausea and/or vomiting despite appropriate antiemetic medication. This medication should be started at the first sign of nausea and/or vomiting (see Section 6.3.2.6)
 |                                      |

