#### 6.3.2.2 Guidelines for the follow-up of liver laboratory abnormalities

In patients with any clinically relevant liver laboratory abnormality, as defined below, hepatic toxicity monitoring must include **ALL** of the following LFTs: albumin, ALT, AST, total bilirubin (fractionated if total bilirubin  $>$  1.5x ULN, and any additional evaluation suggested by these results should be performed as clinically indicated), ALP. Note: for patients with Gilbert Syndrome, total and direct bilirubin must be monitored, but intensified monitoring applies to changes in direct bilirubin only.

In case of any occurrence of ALT/AST/total bilirubin increase to grade 2, the LFTs must be monitored weekly (or more frequently if clinically indicated) until the event resolves to  $\leq$  grade 1. Thereafter monitoring must be continued every 2 weeks (or more frequently if clinically indicated) for two additional cycles (e.g. 6 weeks). If there is no recurrence of  $\geq$  grade 2 ALT/AST/total bilirubin elevations during this period, subsequent monitoring must be performed every 3 weeks. For patients with liver metastasis and grade 2 AST/ALT at baseline, increased monitoring is required for grade 3/4 AST/ALT; follow guidelines for grade 3 or 4 AST/ALT.

In case of any occurrence of ALT/AST/total bilirubin increase to grade 3 or 4, LFTs must be monitored weekly (or more frequently if clinically indicated) until the event resolves to  $\leq$  grade 1. Thereafter monitoring must be continued every 2 weeks (or more frequently if clinically indicated) for four additional cycles (e.g., 12 weeks). If there is no recurrence of  $\geq$  grade 2 ALT/AST/total bilirubin elevations during this period, subsequent monitoring must be performed every 3 weeks.

Patients who discontinue study treatment due to liver toxicity must be monitored weekly (or more frequently if clinically indicated) until the event resolves to  $\leq$  grade 1 or stabilization occurs (no CTCAE grade change over 3 weeks). Refer to Table 6-5.

Patients with transaminase increase combined with total bilirubin (TBIL) increase may be indicative of potential DILI, and should be considered as clinically important events.

The threshold for potential DILI may depend on the patient's baseline AST/ALT and TBIL value; patients meeting any of the following criteria will require further follow-up as outlined below:

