- For patients with normal ALT and AST and TBIL value at baseline: AST or ALT > 3.0 x ULN combined with TBIL > 2.0 x ULN
- For patients with elevated AST or ALT or TBIL value at baseline: [AST or ALT > 2 x baseline AND > 3.0 x ULN] OR [AST or ALT > 8.0 x ULN], combined with [TBIL > 2 x baseline AND > 2.0 x ULN]

Medical review needs to ensure that liver test elevations are not caused by cholestasis, defined as: ALP elevation > 2.0 x ULN with R value (ALT/ALP in x ULN) < 2 in patients without bone metastasis, or elevation of ALP liver fraction in patients with bone metastasis.

Note: (The R value is calculated by dividing the ALT by the ALP, using multiples of the ULN for both values. It denotes the relative pattern of ALT and/or ALP elevation is due to cholestatic or hepatocellular liver injury).

In the absence of cholestasis, these patients should be immediately discontinued from study drug treatment, and repeat LFT testing as soon as possible, preferably within 48 hours from the awareness of the abnormal results. The evaluation should include laboratory tests, detailed history, physical assessment and the possibility of liver metastasis or new liver lesions, obstructions/compressions, etc:

- Laboratory tests should include ALT, AST, albumin, creatinine kinase, total bilirubin, direct and indirect bilirubin, GGT, prothrombin time (PT)/INR and alkaline phosphatase.
- A detailed history, including relevant information, such as review of ethanol, concomitant medications, herbal remedies, supplement consumption, history of any pre-existing liver conditions or risk factors, should be collected.
- Further testing for acute hepatitis A, B, C or E infection and liver imaging (eg, biliary tract) may be warranted.
- Additional testing for other hepatotropic viral infection (CMV, EBV or HSV), autoimmune hepatitis or liver biopsy may be considered as clinically indicated or after consultation with specialist/hepatologist.

All cases confirmed after repeat testing and meeting the laboratory criteria defined above, with no other alternative cause for LFT abnormalities identified should be considered as "medically significant", these cases will meet the definition of SAE ([Section 7.2.1](#)) and reported as SAE using the term "potential drug-induced liver injury". All events should be followed up with the outcome clearly documented.

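### Table 6-4 keeps the dose when bilirubin is >1.5 to ≤2.0 x ULN and both AST and ALT are >3.0 to ≤5.0 x ULN, although lower and higher transaminases both lead to a hold

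*Protocol*

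**What the plan says.** Section 6.3.1, Table 6-4, treats bilirubin and transaminases in separate blocks, followed by two rows for concurrent elevation.

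- The bilirubin Grade 2 row reads "Grade 2 (> 1.5 and ≤ 3.0 x ULN) with ALT or AST ≤ 3.0 x ULN". Its action is to omit dosing until Grade 1 or lower, then resume at the same dose if that took 7 days or less, or one level lower if longer. In Gilbert syndrome, "for patients with Gilbert Syndrome these dose modifications apply to changes in direct [conjugated] bilirubin only".
- The AST/ALT Grade 2 row reads "Grade 2 (> 3.0 and ≤ 5.0 x ULN) without total bilirubin elevation to > 2.0 x ULN". Its action is to keep the dose and monitor liver tests.
- The AST/ALT Grade 3 and Grade 4 rows (above 5.0 x ULN, bilirubin not above 2.0) omit dosing and then reduce one level.
- The first concurrent row needs bilirubin above 2.0 x ULN without cholestasis or hemolysis, and discontinues permanently. The second needs AST or ALT above 5.0, and discontinues if the event recurs after a reduction.

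Section 6.3.2.2 requires at least weekly liver tests for any Grade 2 rise and adds: "Patients with transaminase increase combined with total bilirubin (TBIL) increase may be indicative of potential DILI, and should be considered as clinically important events".

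**The concern.** The bilirubin hold stops applying once both transaminases pass 3.0 x ULN. The rows meant to take over start at bilirubin above 2.0 or transaminases above 5.0. Between those limits only a keep-the-dose row is left. A dose rule should not become more permissive as the liver panel worsens, least of all for a combination that Section 6.3.2.2 calls clinically important.

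What is at stake is patient safety: a child with the worse panel stays on full daily dosing while one with a milder panel is held. By Amendment 8 all patients had completed at least 6 cycles. Under Section 7.2.2.5.2, scheduled chemistry from cycle 5 on falls only on Day 1 of each 21-day cycle, so the table's instruction at that visit is the one that operates.

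**Working it through.** The plan states no figure to reproduce. The check applies every hepatic row of Table 6-4 to fixed values in a patient without Gilbert syndrome at first detection.

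**Bilirubin fixed at 1.8 x ULN, both transaminases rising**

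| AST and ALT (x ULN) | Matching rows | Action |
|---|---|---|
| 2 and 2 | bilirubin Grade 2; AST/ALT Grade 1 | omit |
| 4 and 4 | AST/ALT Grade 2 only | maintain |
| 6 and 6 | AST/ALT Grade 3; second concurrent row | omit, reduce one level; discontinue if it recurs after reduction |
| 21 and 21 | AST/ALT Grade 4 | omit, reduce one level |

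Bilirubin of 1.6 and 2.0 gives the same sequence. The switch points are 3.0 (3.1 is already maintain) and 5.0 (5.1 is again omit).

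In the first line a maintain row also matches, but a maintain for one abnormality does not cancel a hold ordered for another. Grade 2 nausea, for example, carries "Maintain dose level but adjust anti-emetic treatment", and nobody would read that as overriding the hold for Grade 2 diarrhea.

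**Transaminases fixed at 4 x ULN, bilirubin rising**

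- Bilirubin 1.4: maintain.
- Bilirubin 1.8: maintain.
- Bilirubin 2.1: permanent discontinuation, absent cholestasis or hemolysis.

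There is no intermediate step.

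**One transaminase above 3.0, the other not (bilirubin 1.8, values 4 and 2)**

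If the qualifier in the bilirubin row means that either enzyme may be at or below 3.0, the row matches and dosing is omitted. If it means both, only the maintain row is left. The wording allows both readings. The case with both enzymes above 3.0 comes out the same under either.

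**Does other text repair it?**

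- The general guidelines in Section 6.3.1 cover only toxicities that Table 6-4 does not list.
- The table footnote, "All dose modifications should be based on the worst preceding toxicity", selects no hold, because both abnormalities are Grade 2 and the bilirubin row's own condition is not met.
- Section 6.3.2.2 adds monitoring. Its potential-DILI criterion for patients with normal baseline values starts at "AST or ALT > 3.0 x ULN combined with TBIL > 2.0 x ULN", and the criterion for elevated baselines also needs bilirubin above 2.0.
- Section 6.1.3 lets the investigator stop treatment, which is discretion and not a correction of the written instruction.

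**Exposure**

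Dosing is once daily and rechecks are at least weekly: 1 dose per day x 7 days = up to 7 doses before each recheck. If the recheck is unchanged, the same row again says maintain.

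**The case against.** The strongest reply is that the row is explicit and not an omission. Its bilirubin limit of 2.0 x ULN matches the concurrent discontinuation row and the potential-DILI criteria, and Amendment 5 aligned this section with other LDK378 protocols. Weekly tests apply, the investigator may stop treatment, and Section 12.1 expects immediate safety action even where it deviates from the protocol.

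All of this bears on weight and supports a minor grading. It does not explain the inversion. A limit of 2.0 might justify keeping the dose if Grade 2 bilirubin were tolerated below it, but the same table holds such patients when their transaminases are lower. Shared wording across protocols gives no reason for that.

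Three stronger inferences are not supported:

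- A reader might count enzyme pairs and call this one isolated cell. With values of 2, 4, 6 and 25 x ULN at bilirubin 1.8, 15 of 16 pairs are held under the either-enzyme reading and 13 of 16 under the both-enzymes reading. The count depends on the chosen values and the reading, so it does not measure size.
- A reader might take 7 doses as the most that can be given. Seven runs only to the next check; an unchanged panel has no fixed limit.
- A reader might infer that the RDE is biased, because the Table 6-2 DLT criterion also names Grade 2 bilirubin only with Grade 1 AST or ALT. The documents report no such case, Table 6-4 is not an input to the dose-toxicity model, and Table 6-2 lets investigators and sponsor classify other unacceptable toxicities as DLTs.

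**Conclusion.** The rule is wrong as written, and the point is minor. It holds for patients without Gilbert syndrome, at first detection, with total bilirubin >1.5 to ≤2.0 x ULN and both transaminases >3.0 to ≤5.0 x ULN. With one transaminase above 3.0 and up to 5.0 and the other not above 3.0, the action depends on how the qualifier is read.

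The affected range lies below the potential-DILI threshold, and the documents do not say how often it occurs. Recruitment is complete, so under the current version at most the twelve patients on treatment at Amendment 8 are concerned. No effect on the RDE, efficacy or any other endpoint is claimed.

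**What to change.** Three changes to Table 6-4:

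1. Limit the AST/ALT Grade 2 maintain row to total bilirubin ≤1.5 x ULN. For Gilbert syndrome, use direct bilirubin ≤1.5 x ULN and keep the present total limit of 2.0. Without this clause, a Gilbert patient with total bilirubin 1.8, normal direct bilirubin and both enzymes at 4 x ULN would match no row.
2. Add a concurrent row: AST or ALT >3.0 and ≤5.0 x ULN, neither >5.0, with total bilirubin >1.5 and ≤2.0 x ULN (Gilbert: direct bilirubin >1.5 with total ≤2.0). Action: omit until bilirubin is Grade 1 or lower; same dose if resolved in ≤7 days, one level lower if >7 days. This also settles the one-enzyme case.
3. Add a note that where several rows match, the stricter action applies.

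Leave the bilirubin Grade 2 row otherwise unchanged. Dropping its enzyme qualifier looks simpler, but it would also capture bilirubin above 2.0 with cholestasis or hemolysis and both enzymes above 3.0, where no first-occurrence row now matches. Such a patient with enzymes of 6 or 25 x ULN could then restart at full dose within 7 days, while bilirubin 1.8 with enzymes of 6 requires a reduction. That gap is separate and this fix does not address it.

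The cost is a written amendment under Section 12.1, some departure from the wording shared with other LDK378 protocols, and an occasional extra dose hold. Amendment 8 already edited Table 6-4, so the change can go with any further edit.

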## 5.3 Exclusion criteria

Patients eligible for this study must not meet **any** of the following criteria:

1. Patients with symptomatic central nervous system (CNS) metastases who are neurologically unstable or require increasing doses of steroids or local CNS-directed therapy (such as radiotherapy, surgery or intrathecal chemotherapy) to control their CNS disease.

2. Patients with clinically significant, uncontrolled heart disease or corrected QT (QTc) interval > 480 milliseconds, using the Fridericia correction (QTcF).
3. Patients with the following laboratory values during screening:
  - Creatinine > 1.5 x ULN for age.
  - Total bilirubin > 1.5 x ULN for age, except for patients with Gilbert's syndrome, who may be included if total bilirubin is  $\leq 3.0$  x ULN and direct bilirubin is  $\leq 1.5$  x ULN.
  - Alanine aminotransferase (ALT) > 3 x ULN for age, except for patients that have tumor involvement of the liver, who must have a value  $\leq 5$  x ULN.
  - Serum aspartate aminotransferase (AST) > 3 x ULN for age, except for patients that have tumor involvement of the liver, who must have a value  $\leq 5$  x ULN.
  - Absolute neutrophil count (ANC) <  $0.75 \times 10^9/L$  without use of granulocyte growth factor for  $\geq 14$  days.
  - Platelet count <  $50 \times 10^9/L$ .
  - Hemoglobin (Hgb) < 8 g/dL.
  - Alkaline phosphatase (ALP) > 5.0 x ULN
  - Serum amylase > 2 x ULN
  - Serum lipase > ULN
  - Fasting plasma glucose  $\geq 175$  mg/dL ( $\geq 9.8$  mmol/L)
  - Potassium, magnesium, calcium or phosphate abnormality > CTCAE grade 1.
4. Body surface area (BSA) <  $0.35 \text{ m}^2$ .
5. Impairment of gastrointestinal (GI) function or GI disease that may significantly alter the absorption of LDK378 (e.g., ulcerative diseases, uncontrolled nausea, vomiting, diarrhea, or malabsorption syndrome).
6. Evidence of active viral hepatitis, including Hepatitis A, B or C (testing for viral hepatitis is not mandatory).
7. Known diagnosis of human immunodeficiency virus (HIV) infection (HIV testing is not mandatory).
8. Presence of  $\geq$  CTCAE grade 2 toxicity (except alopecia, peripheral neuropathy, ototoxicity and lymphopenia, which are not excluded if grade 3 or less) due to prior cancer therapy.

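### Two liver stop rules need tidying: Table 6-4's combined AST/ALT and bilirubin rows overlap with no stated precedence, and Section 6.3.2.2 omits the hemolysis exemption that Table 6-4 gives

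*Protocol*

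**What the plan says.** Protocol Table 6-4 (Section 6.3.1) has a block for concurrent AST/ALT and total bilirubin (TBIL) elevation with two rows.

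- Row 1: "AST or ALT > 3.0 x ULN with total bilirubin > 2.0 x ULN in the absence of cholestasis or hemolysis". The action is permanent discontinuation, with a reference to Section 6.3.2.2 for follow-up.
- Row 2: "AST or ALT > 5.0 and ≤ 20.0 x ULN with total bilirubin > 1.5 and ≤ 3.0 x ULN". The action is "Permanently discontinue patient from LDK378 if event reoccurs after dose reduction". The row has no cholestasis or hemolysis qualifier and gives no action for a first event.

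The AST/ALT block above them has a row for "Grade 3 (> 5.0 and ≤ 20.0 x ULN) without total bilirubin elevation to > 2.0 x ULN", with the action to omit the dose until Grade 1 or less and then go down one dose level.

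Section 6.3.2.2 sets its own criteria for possible drug-induced liver injury. With normal baseline values these are AST or ALT above 3.0 x ULN with TBIL above 2.0 x ULN, the same thresholds as row 1. It then says: "In the absence of cholestasis, these patients should be immediately discontinued from study drug treatment". Hemolysis is not mentioned.

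The hepatic DLT criterion in Table 6-2, like row 1, exempts both cholestasis and hemolysis.

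**The concern.** These are permanent-stop rules for children whose disease has progressed on standard therapy or has no effective standard therapy. Sites need one answer for each set of laboratory values.

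In the overlap of rows 1 and 2, one row says stop now and the other speaks only of stopping later, after a reduction. A site that goes to the row matching its exact range could take row 2 as permission to reduce and continue a child who meets row 1's stop criterion.

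On hemolysis the risk runs the other way. Table 6-4 spares a child whose bilirubin rise comes from red-cell breakdown, but the section to which row 1 refers takes that child off drug.

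**Working it through.** The plan gives no figure to reproduce, so the check is logical. All values are multiples of ULN.

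**Overlap.** Row 1 needs AST/ALT > 3.0 and TBIL > 2.0, with no cholestasis or hemolysis. Row 2 needs AST/ALT > 5.0 to 20.0 and TBIL > 1.5 to 3.0. The intersection is AST/ALT > 5.0 to 20.0 with TBIL > 2.0 to 3.0.

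**Is a reduction ordered there?** Row 2 presupposes one.
- The Grade 3 AST/ALT row requires TBIL not above 2.0, so it is excluded.
- The Grade 4 AST/ALT row starts above 20.0, so it is excluded.
- The Grade 2 Total Bilirubin row requires ALT or AST at or below 3.0, so it is excluded when the two enzymes move together.

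On a grid in 0.1 steps with AST = ALT, the overlap has 150 x 10 = 1,500 combinations, and none meets another AST/ALT or Total Bilirubin row. If one enzyme stays at or below 3.0, the Total Bilirubin row could be read as met, which adds a further possible action.

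**Example patients** (normal baseline, AST = ALT):

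| AST/ALT | TBIL | Cause of TBIL rise | Table 6-4 | Section 6.3.2.2 |
|---|---|---|---|---|
| 8 | 1.8 | neither | Grade 3 row: omit, then reduce; row 2: stop on recurrence | criteria not met |
| 8 | 2.5 | neither | row 1: stop now; row 2: stop on recurrence | discontinue |
| 8 | 2.5 | hemolysis | row 1 exempt; row 2 met, no first-event action | discontinue |
| 4 | 2.5 | hemolysis | row 1 exempt; no other hepatic row applies | discontinue |
| 4 | 2.5 | cholestasis | row 1 exempt; no other hepatic row applies | exempt |

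The first line shows that the table works for TBIL > 1.5 to 2.0. The second is the overlap. The third and fourth are the hemolysis mismatch. The fifth shows that the two places agree on cholestasis.

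**Frequency, outside Gilbert syndrome.** Protocol Section 2.6 reports concurrent ALT > 3 and TBIL > 2 with normal alkaline phosphatase in under 1% of patients in clinical studies. Amendment 8 gives 83 treated and 12 still on drug. Taking 0.1% to 1% as an assumed range:
- 83 x 0.001 to 83 x 0.01 = 0.08 to 0.83 patients treated
- 12 x 0.001 to 12 x 0.01 = 0.01 to 0.12 patients still on drug

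The overlap (higher AST/ALT, capped TBIL) and the hemolysis cases are each only part of such events. The figures assume that children have the rate of the earlier studies.

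**The case against.** **Stopping complies with everything.** Row 2 never orders or permits continuation at a first event, and a patient stopped under row 1 cannot reach row 2's condition. A footnote to Table 6-4 also bases all modifications on the worst preceding toxicity, which favors the stricter row. This stands. A reader might infer that the two rows contradict each other, so that a site must breach one, and the text does not support that. What remains is that precedence is unstated and row 2 refers to a reduction that no AST/ALT row orders at that bilirubin level.

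**Row 1's hemolysis qualifier only limits row 1.** The table does not order continuation, so following Section 6.3.2.2 breaches nothing. That is formally right, but the exemption then has no effect, because row 1's thresholds are those of Section 6.3.2.2 for a normal baseline. Table 6-2 exempts hemolysis too, so Section 6.3.2.2 is the outlier. Its later condition about other causes governs SAE classification after repeat testing, not the immediate stop.

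**Other text fills the gap.** The general guidelines in Section 6.3.1 say to interrupt and then reduce for non-life-threatening Grade 3 or 4 treatment-related toxicity, but their heading limits them to toxicities not listed in Table 6-4. Section 6.2.4 orders a hold and usually a lower dose after a DLT, but a DLT is a Cycle 1 event. Neither is a clean fallback.

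**Gilbert syndrome.** A reader might infer a third contradiction. Section 5.3 excludes raised bilirubin "except for patients with Gilbert's syndrome, who may be included if total bilirubin is" no more than 3.0 x ULN (with a limit on direct bilirubin). The note "for patients with Gilbert Syndrome these dose modifications apply to changes in direct [conjugated] bilirubin only" sits on the Total Bilirubin heading, and the footnote beginning "If Grade 3 or 4 hyperbilirubinemia is due to the indirect (non-conjugated) component only, and hemolysis as the etiology has been ruled out" starts at Grade 3. Neither reaches row 1, so an ALT rise alone could trigger it in a child who enters with TBIL above 2.0. But no text contradicts row 1, and a carve-out would loosen a liver-safety stop. The documents do not say that any Gilbert patient enrolled, so the effect cannot be sized.

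**Raised baseline.** Section 6.3.2.2 uses narrower thresholds for raised baseline values. This is not a contradiction either, since stopping under Table 6-4 satisfies both.

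**Conclusion.** Wrong as written on two counts, and minor. The overlap is an ambiguity with a safe reading, which is to stop under row 1. The hemolysis mismatch is a real difference: the same child is discontinued under Section 6.3.2.2 and exempt under Table 6-4. The missing Gilbert allowance on row 1 is a scope question for the sponsor's safety review.

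Few patients are affected: outside Gilbert syndrome, fewer than one of the 83 treated would be expected to have such an elevation if the under-1% rate carries over to children. A reader might take the share of row 2's bilirubin range that row 1 also covers, (3.0 - 2.0)/(3.0 - 1.5) = 2/3, as the size of the problem. It measures threshold width and says nothing about how many patients fall there.

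The primary endpoint is untouched. DLTs are defined separately in Table 6-2, and SAP Section 2.5 already records the fasted and fed doses as 510 and 500 mg/m².

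**What to change.** - Limit row 2 to TBIL > 1.5 to 2.0 x ULN, plus the cases row 1 exempts for cholestasis or hemolysis.
- State the first-event action for those exempt cases: omit until Grade 1 or less, then reduce one dose level, as in the Grade 3 AST/ALT row. Say whether this also covers exempt cases with AST/ALT > 3.0 to 5.0, which no hepatic row now reaches when AST and ALT are both in that range.
- Add hemolysis beside cholestasis in the discontinuation sentence of Section 6.3.2.2.
- State that Table 6-4 governs dosing and Section 6.3.2.2 governs the liver-injury work-up and SAE reporting.
- Refer the question of a Gilbert allowance on row 1 to the sponsor's safety review.

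The first four changes cost protocol wording and a clarification to sites, with no new test or visit. With recruitment closed, the direct benefit is to the children still on drug, and to any rollover protocol if it reuses this table.
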